9.3 Timing, Frequency, and Method of Capturing Adverse Events and Serious Adverse Events

9.3.1 Adverse Event Reporting Period

After the ICF has been signed but prior to the administration of the study drug, only SAEs should be reported to the sponsor.

After initiation of study drug, all AEs and SAEs, regardless of relationship to pamiparib or placebo, will be reported until 30 days after the last dose of study drug or initiation of new anticancer therapy, whichever occurs first. After this period, the investigator should report any SAEs that are believed to be related to prior study treatment.

After a patient is discontinued from the study, investigators are not obligated to actively seek AEs or SAEs from the former patient. However, if the investigator learns of any SAE, including a death, at any time, and considers the SAE related to pamiparib, the investigator will notify the sponsor.

9.3.2 Eliciting Adverse Events

The investigator or designee will ask patients about AEs by asking the following standard questions:

- How are you feeling?
- Have you had any medical problems since your last visit?
- Have you taken any new medicines since your last visit?

9.4 Study-Specific Adverse Event and Serious Adverse Event Reporting Instructions

9.4.1 Disease Progression

“Disease progression” (including fatal disease progression), which is expected in this study population and measured as an efficacy endpoint, should not be reported as an event term. Instead, the symptoms, signs, or clinical sequelae that result from disease progression should be reported as the event terms.

For example, a patient presents with pleural effusion resulting from disease progression of metastasis to lungs. The event term should be reported as “pleural effusion” instead of disease progression. If a patient experienced a fatal multiorgan failure due to disease progression, the term “multiorgan failure” should be reported as the SAE with death as outcome instead of reporting “fatal disease progression” or “death due to disease progression”.

9.4.2 Death

Death is an outcome and not usually considered an event. If the only information available is death and the cause of death is unknown, then the death is reported as an event, eg, “death,” “death of unknown cause,” or “death unexplained.”

9.5 Prompt Reporting of Serious Adverse Events

9.5.1 Timeframes for Submitting Serious Adverse Events

If serious adverse events are identified by or reported to the investigator or study team, the SAEs will be reported within 24 hours of first knowledge of the SAEs to the sponsor or designee as described in [Table 3](#) once the investigator determines that the AE meets the protocol definition of an SAE.

Table 3: Timeframes and Documentation Methods for Reporting Serious Adverse Events to the Sponsor or Designee

Type of SAE	Initial SAE Report	Document	Follow-up SAE and AE of Special Interest Report	Reporting Method
All SAEs	Within 24 hours of first knowledge of the SAE	SAE report	As expeditiously as possible	Email or fax SAE form or Pregnancy form

Abbreviations: AE = adverse event; SAE = serious adverse event.

9.5.2 Completion and Transmission of the Serious Adverse Event Report

Once an investigator becomes aware that an SAE has occurred in a patient, he/she will report the information to the sponsor within 24 hours as outlined in [Section 9.5.1](#). The SAE report will always be completed as thoroughly as possible with all available details of the SAE and forwarded to the sponsor or designee within the designated timeframes. The paper SAE form, signed by the investigator, should be scanned and faxed and/or e-mailed to IQVIA. The original SAE form should then be filed appropriately, along with proof of reporting.

If the investigator does not have all information regarding an SAE, he/she is not to wait to receive additional information before notifying the sponsor or designee of the SAE and completing the form. The form will be updated when additional information is received.

The investigator will always provide an assessment of causality at the time of the initial report as described in [Section 9.1.3](#).

The sponsor will provide contact information for SAE receipt.

9.5.3 Regulatory Reporting Requirements for Serious Adverse Events

The investigator will promptly report all SAEs to the sponsor in accordance with the procedures detailed in [Section 9.5.2](#). The sponsor has a legal responsibility to notify, as appropriate, both the

local regulatory authority and other regulatory agencies about the safety of a product under clinical investigation.

The investigator, or responsible person according to local requirements, will comply with the applicable local regulatory requirements related to the reporting of SAEs to regulatory authorities and the IRB/IEC.

All suspected unexpected serious adverse reactions (as defined in [Section 9.6](#)) will be submitted to all applicable regulatory authorities and investigators for pamiparib studies.

When a study center receives an initial or follow-up safety report or other safety information (eg, revised IB) from the sponsor, the investigator or designated responsible person is required to promptly notify his/her IRB or IEC. The investigator should place copies of safety reports from the sponsor in the Investigator Site File.

9.6 Suspected Unexpected Serious Adverse Reactions and Expedited Reporting

A suspected unexpected serious adverse reaction is a serious adverse reaction that is both unexpected (ie, not present in the product's Reference Safety Information in the IB) and assessed as related to pamiparib either by the investigator or the sponsor. The sponsor will promptly assess the expectedness for all SAEs against the list of expected serious adverse reactions in the Reference Safety Information and expeditiously submit suspected unexpected serious adverse reactions to regulatory authorities, investigators, IRBs, and IECs based on applicable legislation.

9.7 Pregnancy Reporting

If a female patient or the partner of a male patient becomes pregnant while receiving study drug or within 6 months after completion of the last dose of study drug, a pregnancy report form is required to be completed and expeditiously submitted to the sponsor to facilitate outcome follow-up. Information on the status of the mother and child will be forwarded to the sponsor. Generally, follow-up will be no longer than 6 to 8 weeks following the estimated delivery date. Any premature termination of the pregnancy will be reported.

While pregnancy itself is not considered to be an AE or SAE, any pregnancy complication or elective termination of a pregnancy for medical reasons will be recorded as an AE or SAE.

An abortion, whether accidental, therapeutic, or spontaneous, should be always reported as an SAE. Similarly, any congenital anomaly/birth defect in a child born to a patient exposed to study drug should be recorded and reported as an SAE.

10 DATA HANDLING AND QUALITY ASSURANCE

This study will be organized, performed, and reported in compliance with the protocol, standard operating procedures, working practice documents, and applicable regulations and guidelines. Study center audits may be made periodically by the sponsor's or the contract research organization's qualified compliance auditing team, which is an independent function from the study team responsible for conduct of the study.

10.1 Data Collection

Data will be entered into the eCRFs in an electronic data capture (EDC) system.

Data collection on the eCRF must follow the instructions described in the eCRF completion guidelines. The investigator has ultimate responsibility for the collection and reporting of all clinical data entered on the eCRF. The investigator or designee must sign the completed casebooks to attest to its accuracy, authenticity, and completeness.

Data contained in the eCRFs are the sole property of BeiGene and should not be made available in any form to third parties without written permission from BeiGene, except for authorized representatives of BeiGene or appropriate regulatory authorities.

10.2 Data Management/Coding

All final patient data, both eCRF and external data (eg, laboratory data), collected according to the protocol, will be stored at BeiGene at the end of the study.

Standard procedures (including following data review guidelines, computerized validation to produce queries, and maintenance of an audit file, which includes all database modifications) will be followed to support accurate data collection. Data will be reviewed for outliers, logic, data inconsistencies, and completeness.

During the course of the study, a study monitor will make study center visits to review protocol compliance, compare eCRFs against individual patient's medical records, and ensure that the study is being conducted according to pertinent regulatory requirements.

eCRF entries will be verified with source documentation. The review of medical records will be performed in a manner to ensure that patient confidentiality is maintained. Checking the eCRFs for completeness, clarity, and cross checking with source documents is required to monitor the progress of the study. Direct access to source data is also required for inspections and audits, and will be carried out giving due consideration to data protection and medical confidentiality.

The monitor will review the eCRFs and evaluate them for completeness and consistency. The eCRF will be compared with the source documents to ensure that there are no discrepancies between critical data. All entries, corrections, and alterations are to be made by the responsible investigator or his/her designee. The monitor cannot enter data in the eCRFs. Once clinical data have been entered into the eCRF, any corrections or alterations to the data fields will be traceable

via an audit trail, meaning that the reason for change, the name of the person who performed the change, together with time and date will be logged. Roles and rights of the study center personnel responsible for entering the clinical data into the eCRF will be determined in advance. If additional corrections are needed, the responsible monitor or data manager will raise a query in the EDC application. The appropriate study center personnel will respond to any queries raised.

The eCRF is essentially considered a data entry form and should not constitute the original (or source) medical records unless otherwise specified. Source documents are all documents used by the investigator or hospital that relate to the subject's medical history, that verify the existence of the subject, the inclusion and exclusion criteria, and all records covering the subject's participation in the study. They include laboratory notes, ECG results, memoranda, pharmacy dispensing records, subject files, etc.

The investigator is responsible for maintaining source documents. These will be made available for inspection by the study monitor at each monitoring visit. The investigator must submit a completed eCRF for each subject who receives the study drug, regardless of the duration. All supportive documentation submitted with the eCRF, such as laboratory or hospital records, should be clearly identified with the study and subject number. Any personal information, including subject name, should be removed or rendered illegible to preserve individual confidentiality.

The eCRF records will be automatically appended with the identification of the creator by means of their unique User ID. Specified records will be electronically signed by the investigator to document his/her review of the data and acknowledgement that the data are accurate. This will be facilitated by means of the investigators unique User ID and password; date and time stamps will be added automatically at the time of the electronic signature. If an entry on an eCRF requires change, the correction should be made in accordance with the relevant software procedures. All changes will be fully recorded in a protected audit trail, and a reason for the change will be required.

AEs will be coded using the Medical Dictionary for Regulatory Activities (MedDRA®) Version 20.10 or higher. Concomitant medications will be coded using the World Health Organization Drug Dictionary. Concomitant diseases/medical history will be coded using the MedDRA Version 20.10 or higher.

10.3 Quality Assurance

To ensure compliance with GCP and all applicable regulatory requirements, the sponsor may conduct a quality assurance audit. Regulatory agencies may also conduct a regulatory inspection of this study. Such audits/inspections can occur at any time during or after completion of the study. If an audit or inspection occurs, the investigator and institution agree to allow the auditor/inspector direct access to the facilities used for this trial and all relevant documents and to allocate his/her time and the time of his/her personnel to the auditor/inspector to discuss findings and any relevant issues.

11 SAMPLE SIZE AND DATA ANALYSES

11.1 Determination of Sample Size

Approximately 24 patients (approximately 12 in each part) will be enrolled to ensure that 20 patients (10 in each part) complete the study.

The sample size chosen for this study was based on precedent set by other PK studies of similar nature and was not based on power calculations.

11.2 Analysis Populations

11.2.1 Pharmacokinetic Population

The PK population will include all patients who received at least 1 dose of pamiparib and have evaluable PK data. A patient will be excluded from the PK summary statistics and statistical analysis if the patient has an AE of vomiting that occurs at or before 2 x median t_{max} .

11.2.2 Safety Population

The safety population will include all patients who received at least 1 dose of pamiparib.

11.3 Pharmacokinetic Analyses

The plasma PK parameters of pamiparib following pamiparib dosing on Days 1 and 10 in Part A and Days 1 and 7 in Part B will be calculated from pamiparib concentration-time profiles using standard noncompartmental methods. Leftover plasma samples may be analyzed for metabolite(s) of interest.

The primary PK parameters are AUC_{0-t} , $AUC_{0-\infty}$, AUC_{0-12} , C_{max} , t_{max} , $t_{1/2}$, CL/F , and V_z/F for pamiparib. Other PK parameters may be reported but will be regarded as secondary and will not be subject to inferential statistical analysis.

A linear mixed-model analysis will be applied to analyze the log-transformed primary PK parameters (AUC_{0-t} , $AUC_{0-\infty}$, and C_{max}) for each part of the study. The model assumes a fixed effect for treatment and a random effect for patient.

Estimates of geometric mean ratios together with the corresponding 90% confidence intervals will be derived for the comparisons of the PK parameters as follows:

- Part A: pamiparib plus rifampin (test) versus pamiparib alone (reference)
- Part B: pamiparib plus itraconazole (test) versus pamiparib alone (reference)

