5.2 Endpoints

5.2.1 Primary Endpoints

The PK outcome endpoints of pamiparib derived from the plasma concentration-time profiles following oral administration of pamiparib on Days 1 and 10 in Part A (rifampin interaction) and Days 1 and 7 in Part B (itraconazole interaction) are as follows:

- maximum observed concentration (C_{max})
- AUC from time zero to time of last quantifiable concentration postdose (AUC_{0-t})
- AUC from zero to infinity ($AUC_{0-\infty}$)
- AUC from zero to 12 hours (AUC_{0-12})
- AUC from zero to 9 hours (AUC_{0-9})

-
- time of the maximum observed concentration (t_{max})
- apparent terminal elimination half-life ($t_{1/2}$)
- apparent oral clearance (CL/F)
- apparent volume of distribution (V_z/F)

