7.0 Overview of Planned Analysis

7.1 Changes from Protocol

There are no changes from protocol.

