16.2 Estimation of Pharmacokinetic Parameters

Patients who experience events that may affect their PK profile (e.g. lack of compliance with dosing) may be excluded from the PK analysis. At the discretion of the pharmacokineticist, a concentration value may also be excluded if the deviation of sampling time from the nominal time is of sufficient concern or if the concentration is anomalous for any other reason.

The following PK parameters will be calculated as data allows for pamiparib concentrations in plasma:

Primary:

Parameter	Description	SAS Programming Notes
C _{max}	Maximum plasma concentration. Observed peak analyte concentration obtained directly from the experimental data without interpolation, expressed in concentration units	C _{max} from WNL
AUC _{last}	Area under the concentration-time curve (time 0 to time of last quantifiable concentration).	AUC _{last} from WNL
AUC _{0-12h}	Area under the concentration-time curve (time 0 to time 12h) as observed.	AUC at tpt=12 h from WNL
AUC _{0-9h}	Area under the concentration-time curve (time 0 to time 9h) as observed.	AUC at tpt=9 h from WNL
AUC _{inf}	Area under the plasma concentration-time curve (time 0 to infinity). Percent extrapolation less than or equal to 20% and an r ² greater than 0.90 are required to retain AUC _{inf} .	AUCINF_obs from WNL If AUC_%Extrap_obs >20% or Rsq ≤ .90 then parameter is deleted
T _{max}	Time to maximum plasma concentration. First observed time to reach peak analyte concentration obtained directly from the experimental data without interpolation, expressed in time units.	T _{max} from WNL

Parameter	Description	SAS Programming Notes
T _{1/2}	Terminal phase half-life expressed in time units. Percent extrapolation less than or equal to 20% and r ² greater than 0.90 is required to retain T _{1/2} .	HL_Lambda_z from WNL If AUC_%Extrap_obs >20% or Rsq ≤ .90 then parameter is deleted
CL/F	Apparent clearance Percent extrapolation less than or equal to 20% and r ² greater than 0.90 is required to retain T _{1/2} .	CL_F_obs from WNL If AUC_%Extrap_obs >20% or Rsq ≤ .90 then parameter is deleted
V _z /F	Apparent volume of distribution during terminal phase Percent extrapolation less than or equal to 20% and r ² greater than 0.90 is required to retain T _{1/2} .	Vz_F_obs from WNL If AUC_%Extrap_obs >20% or Rsq ≤ .90 then parameter is deleted

Note: AUCs are calculated using linear up / log down, expressed in units of concentration x time.

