16.4 Statistics of Pharmacokinetic Parameters

Statistical analyses will be performed to assess the effect of steady-state itraconazole and rifampin on the PK of pamiparib using the treatment in combination with pamiparib as test and the treatment with pamiparib only as reference.

Summary statistics will include number (N), arithmetic mean, standard deviation (SD), %CV, standard error of the mean (SEM), minimum, median, maximum, and geometric mean. For T_{\max} , only n, median, min and max will be presented.

Data for each treatment part will be analyzed separately.

A linear mixed model with a fixed effect for treatment and a random effect for patient will be used on the natural log-transformed parameters C_{\max} , $AUC_{0-\text{last}}$, and $AUC_{0-\text{inf}}$. A point estimate and the corresponding 90% CI for the difference between least squares means of Test and Reference treatment (Test – Reference) will be calculated. The antilogarithm of this value will be calculated to obtain the point estimate and the 90% CI for the ratio (Test/Reference) of the geometric means on the untransformed scale. For each

parameter selected for analysis, patients who do not have valid parameters in both periods will not be included for analysis.

The SAS PROC MIXED code is as follows:

```
proc mixed data = adpp;  
  by parameter;  
  class treatment patient;  
  model ln(aval) = treatment;  
  random patient;  
  lsmeans treatment / alpha = 0.1;  
  estimate "Pamiparib only vs Pamiparib with Itraconazole/Rifampin"  
  treatment -1 1 / e cl alpha=0.1;  
run;
```

For parameters C_{max} , AUC_{0-last} , and AUC_{0-inf} a listing of the individual patient ratios (Test/Reference) will be provided.

A forest plot of the geometric LS mean ratios of C_{max} , AUC_{0-last} , and AUC_{0-inf} will be provided for a visual representation of the data.

All plasma PK parameters will be listed by patient.

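### AUC0-12 (and AUC0-9 in the SAP) is a primary PK endpoint but gets no test/reference ratio or 90% CI, while the AUC0-inf ratio may lose many pairs in Part B

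*Protocol*

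**What the plan says.** **Which parameters are primary.** Protocol 3.1 and 11.3 name eight: Cmax, AUC0-t, AUC0-inf, AUC0-12, tmax, t1/2, CL/F and Vz/F. Of parameters outside that list, Protocol 11.3 says: "Other PK parameters may be reported but will be regarded as secondary and will not be subject to inferential statistical analysis". SAP 5.2.1 keeps the eight, including "AUC from zero to 12 hours", and adds a ninth, "AUC from zero to 9 hours". SAP 7.1 nevertheless states: "There are no changes from protocol".

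**Which parameters are modelled.** Protocol 11.3 says: "A linear mixed-model analysis will be applied to analyze the log-transformed primary PK parameters", and then names only AUC0-t, AUC0-inf and Cmax in brackets. For the comparisons it adds: "Estimates of geometric mean ratios together with the corresponding 90% confidence intervals will be derived". The Synopsis gives the same three. SAP 16.4 matches: "A linear mixed model with a fixed effect for treatment and a random effect for patient will be used on the natural log-transformed parameters", followed by Cmax, AUC0-last and AUC0-inf. The individual-ratio listing and the forest plot cover the same three.

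**Which parameters can be deleted.** For AUC0-inf, SAP 16.2 requires "Percent extrapolation less than or equal to 20" per cent and an r² above 0.90; otherwise the value is deleted. The same rule deletes t1/2, CL/F and Vz/F. Under SAP 16.4 a patient lacking a valid value in either period leaves the comparison for that parameter. No such rule applies to AUC0-t, AUC0-12, AUC0-9 or Cmax.

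**The concern.** The primary objectives are to determine the effect of rifampin and of itraconazole on pamiparib PK. A primary exposure endpoint should therefore carry an estimate of that effect with its uncertainty. Six of the SAP's nine primary parameters do not, and two of the six are exposure measures. Separate summaries for each period give no interval for the paired comparison.

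The gap matters more because one of the two AUCs that are modelled is exposed to deletion. CYP3A inhibition is expected to raise pamiparib concentrations. If it does so by slowing elimination, the half-life lengthens, the extrapolated share of AUC0-inf rises, and Part B loses pairs in the analysis that best measures the interaction. The loss is selective, since profiles with long half-lives go first.

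**Working it through.** The documents give no power or precision figure, so there is none to reproduce.

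**1. Where the 20% limit falls.** Inputs: last sample at 48 h (Protocol Appendix 1); half-life about 13 h, range 5.5 to 34 h (Protocol 1.2.1.1). With mono-exponential decline and a quantifiable 48 h sample, the extrapolated fraction is exp(−ln2 × 48 / t½).

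- Limit: t½ = 48 × ln2 / ln5 = 20.7 h, which is 20.7 / 13 = 1.59 times the documented value.
- Extrapolation is 0.2% at 5.5 h, 7.7% at 13 h, 27.8% at 26 h and 37.6% at 34 h.

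The upper end of the documented range fails on pamiparib alone.

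**2. How many profiles fail.** The documents give neither the half-life distribution nor the size of the inhibition. Assume a log-normal half-life with median 13 h × R, where R is the fold lengthening, and log-SD s. Reading the range as ±2 SD gives s = ln(34/5.5)/4 = 0.46; its upper half alone gives ln(34/13)/2 = 0.48. A smaller value of 0.30 is also shown. The failing fraction is 1 − Φ[ln(20.7 / (13R)) / s].

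| Profile | s = 0.30 | s = 0.48 |
|---|---|---|
| Pamiparib alone (R = 1) | 6% | 17% |
| Test, R = 1.5 | 42% | 45% |
| Test, R = 2 | 78% | 68% |

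If every half-life lengthens by the same factor, the test period decides whether a pair survives. Of 10 Part B completers, about 5.5 to 5.8 pairs remain at R = 1.5. At R = 2 the range is 10 × (1 − 0.78) = 2.2 to 10 × (1 − 0.68) = 3.2. These counts ignore r² failures. In Part A, with half-life halved, under 1% of test profiles fail (s up to 0.47), so losses there come mainly from Day 1.

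**3. What the loss costs in precision.** For n pairs the 90% CI is the ratio multiplied and divided by exp[t(0.95, n−1) × sw × √(2/n)], with sw = √ln(1 + CV²). The within-patient CV is assumed.

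| CV | 10 pairs | 6 pairs | 3 pairs |
|---|---|---|---|
| 20% | 1.18 | 1.26 | 1.60 |
| 30% | 1.27 | 1.41 | 2.01 |
| 50% | 1.47 | 1.73 | 3.08 |

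**4. What a partial AUC would show.** Assume a one-compartment oral model with volume and bioavailability unchanged and ka from 0.5 to 2 per h. Per unit dose and volume, AUC(0–T) = ka/(ka − k) × [(1 − e^(−kT))/k − (1 − e^(−ka·T))/ka].

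Take ka = 1 and a true AUC0-inf ratio of 2.0, so k falls from ln2/13 = 0.0533 to 0.0267 per h:

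- AUC0-12: 9.52 / 8.31 = 1.15
- AUC0-48: 26.79 / 17.22 = 1.56

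Across the ka range:

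| True AUC0-inf ratio | AUC0-9 | AUC0-12 | AUC0-48 |
|---|---|---|---|
| 2.0 | 1.10–1.11 | 1.14–1.15 | 1.55–1.56 |
| 1.5 | 1.06–1.07 | 1.09–1.10 | 1.32–1.33 |
| 0.33 | 0.68–0.71 | 0.61–0.63 | 0.36 |

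Both partial AUCs pull the ratio towards 1 far more than AUC0-48 does.

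**The case against.** The strongest reply is that an exposure ratio already survives. AUC0-t escapes the 20% rule and gets a ratio, a CI, individual ratios and a place in the forest plot; so does Cmax. Step 2 assumes a quantifiable 48 h sample, and on that assumption AUC0-t is AUC0-48 in both periods: a common interval that tracks the effect much better than AUC0-12. This stands. A reader might infer that AUC0-12 is the only primary exposure measure available for all patients. The documents do not support that, for this reason and because AUC0-12 is not guaranteed either. The 9 h and 12 h samples are scheduled for everyone, but parameters are computed only as data allow, concentrations can be excluded, and early vomiting removes the patient.

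A reader might also give AUC0-12 special weight because it spans one twice-daily interval. This is a single-dose comparison: under linear kinetics, steady-state exposure per interval corresponds to single-dose AUC0-inf. In the model AUC0-12 is only 41 to 46% of that, in line with the roughly 2-fold accumulation in Protocol 4.2.

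Nor does the Protocol 11.3 sentence on non-primary parameters itself withhold the ratio. It implies only by contrast that primary parameters are open to inference; the bracketed list after it does the restricting, and the SAP agrees with that list. With no formal hypothesis testing (SAP 9.4.3), the choice of modelled parameters is one of estimation. Geometric means and individual values will also be reported, so with complete pairs the point estimate can be worked out by hand. What is missing is the interval and its display.

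Finally, adding AUC0-12 restores no lost AUC0-inf pair. That is correct, and the fix needs a separate element for it.

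**Conclusion.** The point stands as a mismatch between primary status and planned analysis, worth correcting because the correction is nearly free. AUC0-12 in both documents, and AUC0-9 in the SAP, are declared primary without an interval for the effect they are meant to measure, and AUC0-9 is an undeclared addition to the protocol's list.

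The deletion risk to AUC0-inf is real and falls mainly on Part B. The 20.7 h limit follows from the sampling schedule under mono-exponential decline. The failure rates rest on an assumed half-life spread and on hypothetical 1.5-fold and 2-fold lengthening. At 1.5-fold lengthening or less, the AUC0-inf comparison keeps more than half its pairs on average; at 2-fold it would rest on about two or three.

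It does not follow that the study would lack an exposure ratio, or that AUC0-12 could stand in for AUC0-inf or AUC0-t. Its role can only be supportive.

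**What to change.** 1. In Protocol 11.3 (and the matching Synopsis text) and SAP 16.4, add AUC0-12, and AUC0-9 if it stays primary, to the mixed model, individual-ratio listing and forest plot as supportive results. State beside them that a single-dose partial AUC understates a clearance interaction and does not replace AUC0-inf or AUC0-t.
2. In Protocol 3.1 and 11.3 and SAP 5.2.1 and 16.2, relabel tmax, t1/2, CL/F and Vz/F as descriptive.
3. Declare AUC0-9 in SAP 7.1 as a change from the protocol.
4. In SAP 16.4, report the number of pairs behind each ratio, and add a sensitivity analysis of AUC0-inf that keeps values flagged under the 20% and r² rules. This is the element that addresses the lost pairs.

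Cost: the SAP code already runs by parameter, so item 1 needs one or two more BY-levels, and item 4 a count and one rerun. Sample size is unchanged, and with no hypothesis tested no alpha adjustment arises. The downside is an attenuated supportive estimate, which a reader could take for a weak interaction if its label is unclear.
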